### **Dosage Delays**

The investigator should inform the Amgen Clinical team as soon as the unexpected dosage delay occurs. The following dosage delay rules apply:

- If the dosing delay is  $\leq 3$  weeks, the subject should resume the treatment as soon as possible if deemed safe by the investigator.
- If the dosing delay is more than 4 weeks (missing 1 cycle):
  - Due to treatment related AEs, the subject will be removed from the study.
  - Due to other conditions other than treatment related AEs, the case will be reviewed by Amgen medical monitor to determine whether the subject will be allowed to resume AMG 397 treatment.

### **Rules for Dose Withholding**

AMG 397 should be withheld for any of the following:

- Suspected DLT (including AEs that meet DLT definition outside DLT-observation period)
- Aspartate aminotransferase (AST) or alanine aminotransferase (ALT) greater than 3 x ULN or total bilirubin greater than 1.5 x ULN

### **Rules for Restarting**

AMG 397 dosing can be resumed:

- If the toxicities resolve to grade  $\leq 1$  or return to subjects' baseline values
- Restarting of therapy is deemed safe by the investigators and Amgen's medical monitor.

Approved

## **Rules for Permanent Discontinuation**

Subjects will permanently discontinue from the investigational product if:

- Subjects experience adverse events meeting the DLT criteria at any time. Subjects will be followed until the DLT is resolved, returns to baseline value or is considered stable. Subjects will be withdrawn from AMG 397 treatment and will be treated as deemed appropriate by the investigator or treating physician. Except for:
  - Subjects showing evidence of response or subjects who in the opinion of the investigator may be responding to AMG 397, may have the option to continue therapy once the adverse events recover to baseline or Grade 1 and the re-introduction of AMG 397 is deemed safe by the investigator, Amgen's medical monitor, and Global Safety Officer. The subject should restart at a reduced dose.
  - Subjects who experience TLS as detail, see [Section 6.2.1.1.1](#) for dosing details.
- Intolerability of the study treatment
- The dosing is delayed > 4 weeks due to AMG 397-related adverse events
- Disease progression according to IMWG (MM), Lugano classification (NHL), or 2017 ELN response criteria (AML) and/or per institutional guidelines as applicable
- Clinical significant deterioration of health status
- Withdrawal of informed consent
- Subject becomes pregnant or is breastfeeding
- Initiation of new systemic anti-cancer therapy not provided in this study
- Study is terminated by the sponsor.

### **6.2.1.4 Dose Stopping Rules**

Please refer to [Section 10.4](#) for dose stopping rules.

### **6.3 Other Protocol Required Therapies**

#### **6.3.1 Pre-dosing requirements for AMG 397**

To mitigate risk of TLS, all subjects are to receive TLS prophylaxis prior to first dose of AMG 397 and prior to any dose escalation. Refer to [Section 6.5.7](#) for specific requirements.

### **6.4 Dose Limiting Toxicities**

The grading of adverse events will be based on the guidelines provided in the Common Terminology Criteria for Adverse Events (CTCAE) version 4.03 (available online at <http://evs.nci.nih.gov/ftp1/CTCAE/About.html>). Determination of the severity of adverse events will be consistent with Common Terminology Criteria for Adverse Events (CTCAE) version 4.03.

Approved

**For MM and NHL subjects only:**

A DLT is defined as a treatment-related AE(s), that occur during the DLT-observation period (see [Section 6.2.1.2](#)) including any:

- $\geq$  Grade 3 non-hematological AE's **EXCEPT**:
  - $\geq$  Grade 3 fatigue if  $<7$  days
  - Grade 3 nausea, vomiting and/or diarrhea if  $< 3$  days and controlled with medical management
  - Laboratory parameters of grade  $\geq 3$  that improve with medical management to grade  $\leq 2$  within 3 days
- $\geq$  Grade 4 hematologic AE's AND:
  - $\geq$  Grade 3 neutropenia with fever
  - $\geq$  Grade 3 thrombocytopenia with Grade  $\geq 2$  hemorrhage
  - $\geq$  Grade 3 anemia with symptoms requiring intervention (eg, transfusion)

**NOTE:**  $\geq$  Grade 4 neutropenia must be lasting  $> 7$  days

- Any grade 5 AE that is not clearly due to disease progression

**For AML subjects only:**

Due to the nature of AML, hematologic adverse events will not be considered DLTs. However, prolonged pancytopenia in the presence of a hypocellular bone marrow (ie, cellularity 5% or less without evidence of leukemia) that lasts longer than 42 days will be considered dose-limiting myelosuppression.

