**Non-hematological toxicity:**

- $\geq$  Grade 3 nausea, vomiting or diarrhea persisting more than 3 days despite optimal medical support
- $\geq$  Grade 3 fatigue persisting  $> 7$  days
- Any other  $\geq$  Grade 3 adverse event
- Failure to recover from AMG 397 related toxicities to grade  $\leq 1$  or baseline severity after delaying next cycle up to 14 days

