or adjustment in current therapy are considered adverse events. Where applicable, clinical sequelae (not the laboratory abnormality) are to be recorded as the adverse event.

The investigator is expected to follow reported adverse events until stabilization or reversibility.

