Appendix B. eSerious Event Contingency Form

 Study # 20170173 AMG 397		Electronic Serious Adverse Event Contingency Report Form For Restricted Use																				
Reason for reporting this event via fax The Clinical Trial Database (eg, Rave):  Is not available due to internet outage at my site  Is not yet available for this study  Has been closed for this study																						
FAX # JS: [contact]																						
1. SITE INFORMATION																						
Site Number		Investigator			Country																	
Reporter		Phone Number		Fax Number																		
2. SUBJECT INFORMATION																						
Subject ID Number		Age at event onset		Sex	Race	If applicable, provide End of Study date																
If this is a follow-up to an event reported in the EDC system (eg, Rave), provide the adverse event term: _____ and start date: Day ____ Month ____ Year ____																						
3. SERIOUS ADVERSE EVENT																						
Provide the date the Investigator became aware of this information: Day ____ Month ____ Year ____																						
Serious Adverse Event diagnosis or syndrome If diagnosis is unknown, enter signs / symptoms and provide diagnosis, when known, in a follow-up report  List one event per line. If event is fatal, enter the cause of death. Entry of "death" is not acceptable, as this is an outcome.	Date Started		Date Ended		Check only if event occurred before first dose of IP  Is event serious?   Yes  No	Serious enter Serious Criteria code (see codes below)	Relationship Is there a reasonable possibility that the Event may have been caused by IP or an Amgen device used to administer the IP?	Outcome of Event -Resolved -Not resolved -Fatal -Unknown  Check only if event is related to study procedure eg, biopsy														

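### Read literally, the AML DLT rule leaves out a treatment-related death recorded only under a hematologic term and a short grade 4 or 5 nausea, vomiting or diarrhea event, both of which count in MM/NHL (minor)

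*Protocol*

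**What the plan says.** All of this is in Protocol Section 6.4.

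**MM and NHL.** The lead-in reads "A DLT is defined as a treatment-related AE(s), that occur during the DLT-observation period". The list includes "Any grade 5 AE that is not clearly due to disease progression". It also counts hematologic events of grade 4 or higher, with neutropenia counting only beyond 7 days, and it places "Grade 3 neutropenia with fever" among the hematologic events. The gastrointestinal exemption begins "Grade 3 nausea, vomiting and/or diarrhea if" and requires a duration under 3 days and medical control. It does not cover grade 4 or 5.

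**AML.** "Due to the nature of AML, hematologic adverse events will not be considered DLTs", apart from the 42-day marrow aplasia criterion. Under the non-hematological heading, grade 3 or higher events are DLTs when they are "nausea, vomiting or diarrhea persisting more than 3 days despite optimal medical support". Fatigue has its own duration item. A residual item covers every *other* event of grade 3 or higher, and a last item covers failure to recover after a cycle delay.

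**All subjects.** Clinical tumor lysis syndrome and Hy's Law cases are added. There is no death rule.

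The SAP (Section 5, Dose Limiting Toxicity) defers to the protocol definition.

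**The concern.** The stated reason, the nature of AML, explains leaving cytopenias out. It does not explain leaving out a death attributed to the drug, and it has no bearing on vomiting or diarrhea. Gastrointestinal toxicity is a named risk in Protocol Section 2.2.4, so the second gap falls on a toxicity that was expected.

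DLT status feeds the Group 1B dose-toxicity model and the DLT incidence. An uncounted event is handled in one of two ways under Protocol Sections 6.2.1.2 and 3.4. If the subject received at least 75% of the planned dose, the subject enters as evaluable with no DLT. Otherwise the subject is non-evaluable and may be replaced. Either way the model does not see the event.

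**Working it through.** **1. The two lists side by side**, for an event that is treatment-related and inside the observation period:

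| Event | MM/NHL | AML |
|---|---|---|
| Death under a hematologic term, no 42-day aplasia | DLT (grade 5 clause) | Not a DLT |
| Death under a non-hematologic term outside the gastrointestinal and fatigue items | DLT | DLT (residual item) |
| Grade 4 or 5 nausea, vomiting or diarrhea, 3 days or less, nothing else of grade 3 or higher | DLT | Not a DLT |
| Grade 4 nausea, vomiting or diarrhea, 4 days despite optimal support | DLT | DLT |

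The third row depends on reading *other* in the residual item in its ordinary sense. Nausea, vomiting and diarrhea of grade 3 or higher already have their own item, so a short event is not an *other* event. A site that read the residual item as including it would count the event.

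**2. Evaluability.** A cycle has 8 doses, on days 1, 2, 8, 9, 15, 16, 22 and 23. 75% of 8 is 6, so without lead-in dosing the threshold is reached on day 16. A subject with such an event who stopped before then could be replaced. One who stopped later would count as no DLT.

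**3. Effect on the model.** The plan gives no figure for this point. Its nearest DLT figure, 27 to 70% in Protocol Section 10.3, reproduces: 1 - 0.90³ = 0.271 and 1 - 0.67³ = 0.699.

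Inputs from Protocol Section 10.4:
- Model: logit(p) = log a + exp(log b) · log(d/640).
- At 80 mg: P(rate ≤ 0.40) = 0.90, with 0.05 read as the median.
- At 640 mg: P(rate ≤ 0.05) = 0.05, with 0.25 read as the median.
- Overdose limit: P(rate > 0.33) < 0.40, optionally < 0.25.

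At 640 mg the dose term vanishes, so log a has mean ln(0.25/0.75) = -1.099 and SD (-1.099 + 2.944)/1.645 = 1.122, where -2.944 = ln(0.05/0.95). The mean and SD of log b were solved numerically to match the two 80 mg quantiles. The prior correlation is not stated, so 19 values from 0 to -0.9 were used; every fit was exact. The posterior was computed on a grid.

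P(DLT rate > 0.33) at the next planned dose after one counted event, with all lower cohorts clean (range over correlations):

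| Event at | Next dose | Cohort of 2 | Cohort of 3 | Cohort of 4 | 0 of 2 (not counted) |
|---|---|---|---|---|---|
| 80 mg | 160 mg | 0.440-0.487 | 0.334-0.374 | 0.252-0.285 | 0.059-0.071 |
| 160 mg | 320 mg | 0.298-0.357 | 0.189-0.229 | 0.124-0.150 | 0.039-0.059 |
| 320 mg | 640 mg | 0.351-0.4005 | 0.229-0.321 | 0.149-0.282 | 0.089-0.253 |

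- **One event in 2 at 80 mg:** 160 mg is blocked at every correlation, while 80 mg itself passes (0.380-0.398). Counting the event turns escalate into stay.
- **One event in 2 at 320 mg:** the limit is only touched (0.4001-0.4005 at two of the 19 correlations), so no change is claimed.
- **Other seven steps:** the next dose passes 0.40 and keeps the highest target-interval probability among the permitted planned doses, so the recommendation does not change.
- **Optional 0.25 limit:** a counted event at 80 mg blocks 160 mg at all three cohort sizes.

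**4. Later AML parts, only if amendment 4 keeps the wording.** SAP Table 1, which covers Parts 2A and 3, escalates on 0 DLTs. It de-escalates on 1 in 2 and stays on 1 in 3, 4 or 5. One uncounted event would change the guideline decision at those sizes.

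**The case against.** The strongest case against is that little is lost.

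- **Recording rules.** Protocol Section 9.2.1.1 says "Where applicable, clinical sequelae (not the laboratory abnormality) are to be recorded", and the form in Appendix B says "If event is fatal, enter the cause of death". Most deaths during cytopenia should therefore be recorded as the infection or the bleed, which the residual item counts. This stands, and makes the first case uncommon.
- **The model only guides.** The Dose Level Review Team also reviews grade 3 or higher events that are not DLTs (Section 6.2.1.2), the sponsor is notified of grade 3 or higher events within 24 hours (Section 6.2.1.1), and related life-threatening events bar rechallenge (Section 6.2.1.3). This stands too, but taking non-DLT events into account is at the team's discretion.
- **AML is stricter elsewhere.** It has no laboratory exemption, so a separately reported grade 3 electrolyte or renal consequence would count, and the failure-to-recover item can catch lingering toxicity. That narrows the second case without closing it.
- **Part 1 is closed** (SAP Section 2.1), and the SAP follows amendment 4, which was not supplied. This limits what can be changed.

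Three stronger inferences are tempting and not supported:
- That AML deaths in general are not DLTs. Outside the gastrointestinal and fatigue items, non-hematologic deaths are caught.
- That the events disappear from the safety record. SAP Sections 6.1 and 9.6.1 tabulate fatal and grade 3 or higher events by dose level in all dosed subjects, and treatment-emergent events are part of the primary endpoint.
- That these two are the only differences between the lists. There are others, mostly deliberate cytopenia exclusions or day-boundary and control wording.

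**Conclusion.** The gap is real on the text and minor in effect. Two narrow kinds of event that would be DLTs in MM/NHL are not DLTs in AML, and the protocol's stated reason covers neither a drug-related death nor a severe gastrointestinal event. Under the default limit, one clear model decision changes out of nine checked. The documents give no rate for these events and do not say that any occurred, so they do not support a claim that Part 1 escalation went wrong.

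This rests on the ordinary reading of the residual item, on 0.05 and 0.25 as prior medians, and on correlations from 0 to -0.9. It also assumes that the relevant terms can carry grade 4 or 5, which is set by CTCAE 4.03, not among the documents. Whether the later AML parts are affected cannot be checked without amendment 4.

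**What to change.** Make two changes to the AML list in Section 6.4:

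- Add an exception to the hematologic exclusion: any treatment-related grade 5 event is a DLT unless it is clearly the result of disease progression. State that this adds to the residual grade 3 or higher item and does not limit it. The AML list sets no relatedness condition on that item, so a stand-alone clause restricted to related deaths could be read as removing deaths that now count.
- Limit the duration condition for nausea, vomiting and diarrhea to grade 3, so that any grade 4 or higher event counts.

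Apply both to AML in Parts 2A, 2B and 3B if amendment 4 keeps the present wording. For the 12 Part 1B subjects (SAP Section 3.2), flag in the report the DLT status of any related grade 5 event or grade 4 or higher gastrointestinal event, including in non-evaluable or replaced subjects. The planned tables show the events but not that status.

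The cost is two lines of protocol text and one flag or listing. The MM/NHL rule is untouched. AML escalation may be slightly slower.

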### **2.3.1 Dose Selection Rationale**

#### **2.3.1.1 Starting and Maximum Planned Doses**

The proposed AMG 397 doses are 80, 160, 320, and 640 mg. During dose escalation (Part 1), AMG 397 will be given once daily for 2 consecutive days followed by 5 days break and repeated each week for 4 weeks of treatment cycle. One treatment cycle is 28 days in length and includes 8 administrations of AMG 397.

For dose expansion (Part 2), AMG 397 will be given once daily for 2 consecutive days followed by 5 days break and repeated each week for 4 weeks of treatment cycle. One treatment cycle is 28 days in length and includes 8 administrations of AMG 397. The planned dose level(s) for dose expansion (MTD/RP2D) will be determined based on data collected during dose escalation.

The proposed clinical starting dose of 80 mg is based on the highest non-severely toxic dose (HNSTD) noted in a GLP toxicology study in beagle dogs. The HNSTD dose of 15 mg/kg/day in beagle dogs corresponds, per ICH S9 Guidance, to a human daily equivalent dose of 83 mg. AMG 397 human pharmacokinetics (PK) parameters were predicted from a combination of in vitro and in vivo nonclinical data. At the starting dose of 80 mg administered orally once daily for 2 consecutive days followed by 5 days break, the predicted exposure margins of maximum plasma concentration (Cmax) and area under the concentration-time curve (AUC) to the rat STD10 are 116-fold and 211-fold, respectively. The predicted exposure margins of Cmax and AUC to the dog HNSTD are estimated at 15-fold and 15-fold, respectively, at the starting dose administered orally once daily for 2 consecutive days followed by 5 days break.

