**Table 3. Planned Doses per Dose Cohort Level**

Dose Cohort Levels	Dose (mg) PO
1	80
2	160
3	320
4	640

Dose escalation for Group 1A and Group 1B will begin with 2-4 subjects treated at the lowest planned dose level of 80 mg. Dose escalation will follow the planned schedule described above with 2-4 subjects treated in each cohort.

DLRT will convene to review the safety data and determine the appropriate dose to be implemented. Dose escalation/de-escalation decisions will be guided by the BLRM model of dose toxicity. Skipping of planned dose levels is not allowed. Dose escalation decisions will not be made until all subjects in a cohort(s) are monitored through the DLT-observation period of 28 days following treatment initiation. Intermediate dose levels and alternative dosing schedule(s) may be explored based on emerging pharmacokinetic and safety data per the decision of the DLRT.

Dose escalation for both Group 1A and 1B respectively, will continue until any of the following events:

- The highest planned dose level for each group is determined to be safe and tolerable (minimum of 6 evaluable subjects)
- MTDs are identified for each group where BLRM repeats the recommendation of a dose level (minimum of 6 evaluable subjects)
- The maximum of 30 evaluable subjects have been enrolled in each group. If fewer than 6 subjects are treated at the MTD/RP2D, additional subjects may be enrolled to confirm safety and tolerability.

Intermediate doses and alternative dosing schedule(s) may be explored based on emerging pharmacokinetic and safety data as decided by the DLRT.

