#### **6.2.1.2 Dose-cohort Study Escalation and Stopping Rules**

The Dose Level Review Team (DLRT) will convene before decisions to dose escalate or de-escalate is made or when cohorts are suspended per protocol. The DLRT will be composed of select Investigator(s), Amgen medical monitor, Amgen Global Safety Officer or designee, Amgen Clinical Research Study Manager (CRSM) and Biostatistics representative or designee. Additional members may be added as needed (eg, clinical pharmacologist). The DLRT voting members include the Amgen Medical Monitor and Global Safety Officer or designee, in consultation with the investigator(s) or designee. The DLRT members are responsible for dosing decisions, which may include escalation to the next nominal or intermediate dose, de-escalation to a lower nominal or intermediate dose; alternative dose frequencies, continuation, delay or termination of dosing; or repetition or expansion of a cohort; implementation of lead-in dosing, or determination of RP2D. See [Section 3.1](#) for more details regarding the study design and the dose escalation plan for this study.

The DLT-observation period is defined as, at minimum, 28 days after the initial dose of AMG 397. Once lead-in dosing period is initiated, the DLT-observation period is defined as the amount of time for subject(s) for each dose cohort to receive at least 1 week of lead-in dose and 3 weeks of target dose.

A subject is deemed DLT-evaluable if during the DLT-observation period the subject met at least one of the following criteria:

- Received at least 75% of the planned dose of AMG 397
- Experienced a DLT

Available study data, including data collected after the initial DLT-observation period along with demographics, IP administration, medical history, concomitant medications,

adverse events (AE), ECG, vital signs, laboratory results and PK/PD information will be reviewed. In addition to DLTs, all  $\geq$  grade 3 toxicities not meeting DLT criteria will be reviewed and may be considered in DLRT decisions. Modeling of available potential safety risk data (eg, for thrombocytopenia) to predict safety risk for dose escalation decisions may also be considered.

Dose escalation/de-escalation decisions will be guided by the BLRM model of dose toxicity described by [Appendix D](#). An Amgen representative will notify the sites in writing the dosing decision from the DLRM and when a cohort is open to screen new subjects.

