DLTs experienced by subjects after completing the DLT period will be considered in the BLRM design to account for any late onset toxicity.

Dose escalation for each group will continue until any of the following events occur:

- The highest planned dose level is determined to be safe and tolerable (minimum of 6 evaluable subjects)
- MTDs are identified for each group where BLRM repeats the recommendation of a dose level (minimum of 6 evaluable subjects)
- The maximum of 30 evaluable subjects have been enrolled in each group. If fewer than 6 subjects are treated at the MTD/RP2D, additional subjects may be enrolled to confirm safety and tolerability.

If there are concerns about the tolerability of the current dosing schedule, alternative dosing schedules or lower dose(s) may be explored, including modification of the lead-in period dosing regimen. The alternative dose and schedule will be jointly determined by the investigators and the Amgen medical monitor, based on pharmacokinetic and safety and toxicity data.

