## 10.5 Planned Analyses

### 10.5.1 Interim Analyses

Safety data will be reviewed on an ongoing basis. Based on accumulating toxicity information, BLRM will be used to make dosing recommendations. In dose level review team meetings (DLRMs), Amgen, in consultation with the site investigators, will review the BLRM recommended dose level and will review all available cumulative data by cohort prior to making dose escalation decisions. As a sensitivity analysis, a one-parameter Continual Reassessment Method (CRM) model may be used to estimate

the dose-toxicity relationship to help making dose escalation decisions. Adverse events and DLTs observed in all subjects will be evaluated continually and fully integrated into all DLRMs and considered in all enrollment and dosing decisions.

An interim analysis for efficacy parameters will be conducted after dose escalation is completed.

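### In Part 1 AML the only haematological DLT cannot be met before day 43, escalation may be decided after 28 days, and no rule makes the next higher cohort wait for unresolved marrow aplasia

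*Protocol*

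**What the plan says.** Protocol 6.4 excludes haematological events as DLTs in AML, with one exception: pancytopenia with a hypocellular, leukaemia-free marrow (cellularity 5% or less) that "lasts longer than 42 days will be considered dose-limiting myelosuppression". The AML list also has a non-recovery criterion, failure to return to grade 1 or "baseline severity after delaying next cycle up to 14 days".

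Protocol 3.1 lets escalation be decided once every subject in the cohort has been "monitored through the DLT-observation period of 28 days following treatment initiation". Section 6.2.1.2 makes 28 days a minimum, sets no longer period for AML, and with lead-in dosing uses 1 plus 3 weeks. A subject is DLT-evaluable after receiving 75% of the planned dose or having a DLT.

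Several provisions bear on a subject whose aplasia is unresolved at day 28:

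- Grade 3 or higher toxicities "not meeting DLT criteria will be reviewed and may be considered in DLRT decisions" (6.2.1.2).
- The review team's options include "alternative dose frequencies, continuation, delay or termination of dosing" (6.2.1.2).
- Adverse events and DLTs are to be "fully integrated into all DLRMs and considered in all enrollment and dosing decisions" (10.5.1).
- DLTs after the window "will be considered in the BLRM design to account for any late onset toxicity" (6.2.1.2).
- The affected subject's own dosing is withheld for a suspected DLT, inside or outside the window (6.2.1.3).
- The sponsor is told of grade 3 or higher events within 24 hours (6.2.1.1), and counts are repeated every 24 to 48 hours in grade 4 neutropenia (footnote 8 to Tables 4 and 5).

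**The concern.** The window that gates escalation is shorter than the time the one AML haematological DLT needs to declare itself. At the decision, a subject with ongoing aplasia is either in the model as evaluable without a DLT or, if dosing stopped early, not evaluable and replaceable under 3.4. In both cases the event most likely to become the DLT is missing from the likelihood. Section 10.4 has no pending category and no time-to-event weighting.

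Marrow toxicity is a named risk: 2.2.4 reports reduced marrow cellularity in dogs and links it to the primary pharmacology. Planned doses double at each step. Whether new AML subjects receive twice the dose while an earlier subject remains aplastic is left to judgement.

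**Working it through.** **1. The plan's own detection figure.** Section 10.3 gives 27% to 70% for seeing at least one DLT in 3 subjects at true rates of 10% to 33%. This reproduces: 1 − 0.90³ = 0.271 and 1 − 0.67³ = 0.699. It presumes every DLT is readable at the decision. If a share s is late, the formula becomes 1 − (1 − p(1 − s))³. The documents give no s. Assumed values of 10%, 25% and 50% give 25%/65%, 21%/57% and 14%/42% for p = 10%/33%. These are illustrations, not estimates.

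**2. Evaluability.** "One treatment cycle is 28 days in length and includes 8 administrations of AMG 397" (2.3.1.1), on days 1, 2, 8, 9, 15, 16, 22 and 23. Six of 8 is 75%, reached on day 16. A subject held from day 17 is therefore evaluable and counted as no DLT.

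**3. Timing.** AML entry requires more than 5% marrow blasts (4.1), so the joint marrow and blood condition cannot predate dosing. With onset on day k, more than 42 days is first met on day k + 42. Assume the decision falls on day 28 for the last-entered subject and the next subject's screening starts then. First dose is then day 28 + 3 = 31 at the fastest (72 hours of urate-lowering, 6.5.7) or day 28 + 21 = 49 with a full screening window.

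| Onset day | Criterion first met | Days after a day 31 start | Days after a day 49 start |
|---|---|---|---|
| 1 | 43 | 12 | none (6 days before) |
| 8 | 50 | 19 | 1 |
| 15 | 57 | 26 | 8 |
| 28 | 70 | 39 | 21 |

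A full screening closes the gap only for onset up to day 7 (7 + 42 = 49). The non-recovery criterion is also late: 29 + 14 gives about day 43.

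**4. Effect on the BLRM.** Section 10.4 gives four prior conditions but no correlation. Taking 0.05 (80 mg) and 0.25 (640 mg) as medians, log a has mean logit(0.25) = −1.099 and SD (−1.099 + 2.944)/1.645 = 1.122. The mean and SD of log b that give median 0.05 and P(rate ≤ 0.40) = 0.90 at 80 mg are (−0.20, 1.2), (−0.28, 1.7) and (−0.46, 3.2) for correlations of −0.5, −0.25 and 0.

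Posterior probability that the DLT rate exceeds 0.33, as the range over those correlations:

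| Data at 80 mg | At 80 mg | At 160 mg |
|---|---|---|
| 0 of 2 | 0.046–0.049 | 0.060–0.068 |
| 1 of 2 | 0.387–0.398 | 0.440–0.475 |
| 0 of 3 | 0.027–0.029 | 0.038–0.044 |
| 1 of 3 | 0.276–0.292 | 0.335–0.364 |
| 0 of 4 | 0.017–0.018 | 0.024–0.030 |
| 1 of 4 | 0.195–0.212 | 0.252–0.277 |

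Among planned doses without skipping, 160 mg has the higher target-interval probability in every row, so it is chosen whenever the limit allows.

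- Limit 0.40: reading the DLT bars 160 mg only for 1 of 2. If it is unread, the recommendation moves from 80 to 160 mg. For 3 or 4 subjects it is 160 mg either way.
- Limit 0.25: reading the DLT bars 160 mg for 1 of 2, 3 or 4, leaving no dose (2 or 3 subjects) or 80 mg (4 subjects). If it is unread, 160 mg is allowed in all three. The result for 4 is marginal (0.252 to 0.277).

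**The case against.** The strongest reply is that the BLRM only guides. The review team decides on all the data, may wait because 28 days is a minimum, may delay dosing, and would hear of a severe cytopenia within a day. A suspected DLT has formal status for the subject's own dosing, and the event enters the model once it occurs. All of this is correct. It rules out two inferences a reader might draw: that the plan ignores prolonged aplasia, or that such a DLT is lost from the analysis. What remains is narrower: every one of these provisions permits waiting, informs the team or acts later, and none holds the next cohort. The Amendment 1 rationale records that the DLT criteria and the longer window were requested by the FDA, but it does not say how 42 days fits a 28-day window.

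A second reply is that the timing is contrived. A day 31 start needs everything to run at full speed, and a leukaemia-free aplastic marrow on day 1 is implausible. Day 31 is indeed a lower bound. Later onset, however, widens the gap.

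The third reply is that the numerical effect is small. Under the operative 0.40 limit that stands: it would be wrong to infer that one unread DLT generally changes the recommendation.

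Finally, Part 1 is closed, and Parts 2 and 3 use mTPI, so the BLRM figures do not carry forward. That also stands.

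**Conclusion.** The concern holds in limited form. The criterion cannot be met inside the window that gates escalation, and the plan leaves the wait to discretion. The model consequence under the 0.40 limit is confined to cohorts of 2, which the protocol allows; under the optional 0.25 limit it extends to cohorts of 2 to 4. These figures rest on a reconstructed prior, on DLT-free earlier cohorts and on planned doses only. The share of late DLTs is unknown.

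Part 1B enrolled 12 subjects and is closed (SAP 2.1 and 3.2), so the point now bears on how firmly its dose findings can be read. It does not show that any dose decision was wrong. A reader might also infer that the gap persists in current AML dosing. The SAP keeps the 28-day minimum, enrols AML in Parts 2A and 3B, and its Table 1 has no pending category: no DLT in 3 subjects escalates, one stays. But it follows amendment 4, which is not supplied, so carry-over depends on that amendment keeping the 42-day criterion.

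**What to change.** State in Protocol 6.2.1.2 and 10.4:

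- An AML subject whose pancytopenia at day 28 is new or worse than baseline is pending until the scheduled cycle 2 day 1 marrow, taken at about day 29 even if cycle 2 dosing is delayed.
- Cellularity above 5%, or leukaemia, releases the subject.
- Otherwise, dosing of a new cohort above that subject's dose waits until counts recover or the 42-day criterion is met. The 42 days run from the first day of the new or worsened pancytopenia. Screening may continue.
- Unchanged baseline pancytopenia does not trigger the hold, because the entry blood-count limits in 4.1 apply to MM and NHL only.
- Optionally, a cycle 2 delay for other AMG 397-related toxicity is also pending, to about day 43.

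If amendment 4 keeps the criterion, place the same rule beside SAP Table 1 for AML subjects in Parts 2A and 3B.

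The cost falls only on affected cohorts. Dosing waits to onset day + 42, at most day 70: up to 70 − 31 = 39 days beyond the fastest start, or 70 − 49 = 21 days beyond a full screening. The first marrow is already scheduled. Confirming persistence may need one extra marrow, which footnote 25 to Tables 4 and 5 already allows at the investigator's discretion.
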